#### 9.6.2 Staged withdrawal from study

Each participant has the right to withdraw their consent to participate at any time by informing the GLINT team in person, by telephone or in writing. However, it is expected that the investigator will make every effort to understand the participant's barriers to participation and provide reassurance, counselling, education, or other mitigation strategies as necessary.

Participants can opt to discontinue any or all of the following:

- Study medication
- •Follow up via participant questionnaires
- •Follow up by GP questionnaires
- •Registry follow up

Withdrawal of consent is defined as an explicit withdrawal from all forms of follow up.

Any information already provided, results from tests already performed on the participant or their samples will continue to be used in the study. We will document the reasons for withdrawn consent, the attempts by the investigator to mitigate those concerns, and the methods permitted for vital status ascertainment (e.g. contact GP and ONS/NHS tagging) on the Trial Management System Database.

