#### 6 Study Flow Chart

ANNUAL FOLLOW-UP UNTIL END OF STUDY All participants will be sent an annual questionnaire including questions on CVD, cancer and diabetes incidence; adverse events; medication adherence; SF8, EuroQol (EQ5D), treatment satisfaction; health service use in last 12 months; GPs will receive an annual questionnaire regarding vital status; CVD, cancer and diabetes incidence; adverse events; current medication; most recent eGFR value (if present)**	
---	--

\*Note that we do not plan to collect LFTs or B12 at baseline in the full study (following safety results from the feasibility phase); we do not plan to collect creatinine measures during study follow-up, (following safety results from the feasibility phase), although we will ask GPs to supply this value if available \*\* If eGFR < 45ml/min, study medication should be stopped

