# GP/participant questionnaire Mail Out (Issued after 4 months, annually and at end of study)

Participant questionnaire

- Self reported morbidity (CVD, cancer, T2DM)
- Medication adherence
- Health service use in past 12 months
- EuroQoL EQ-5D
- Treatment satisfaction/SF-8
- Self-Adverse events

GP questionnaire

- Vital status i.e. alive or dead
- Morbidity (CVD, cancer, T2DM)
- Current prescribed medication
- Adverse events
- Whether participant has become pregnant

Participants and GPs will be instructed to return the completed questionnaires to the DTU in freepost envelopes. If necessary, reminders will be sent after 4 and 8 weeks for the annual questionnaire. Participants will be contacted by phone if they do not respond to the reminders. Annual questionnaires will not be sent within 4 weeks of the end of study questionnaires being issued.

Participants and GPs will be reminded about the potential risks of taking metformin when they receive their four month questionnaire in the feasibility phase and the annual questionnaire in the full study.

When a participant or GP indicates that a primary or secondary endpoint has occurred following receipt of the annual questionnaire, information on this event will be collected immediately. We will also use information from the Office for National Statistics, the Cancer Registry and Health Episode Statistics to assess whether participants have experienced a study endpoint.

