An extremely rare but potentially serious side-effect of metformin is lactic acidosis. The risk of lactic acidosis is increased among people with chronic kidney disease (CKD stage 3b or worse). Consequently, we will exclude individuals with eGFR<45ml/min and measure creatinine at baseline, three and six months in the feasibility phase. Participants' GPs will be reminded of contraindications to metformin and this rare side effect and the need to discontinue study medication in these eventualities (i) when they are informed that their participant has entered the study; (ii) at the four month questionnaire phase in the feasibility phase; and (iii) annually thereafter when receiving their questionnaire. Written reminders detailing the action to be taken by participants in the event of a severe illness, including renal failure, will be sent to participants at four month questionnaire phase in the feasibility phase and every twelve months when they receive their annual questionnaire. Any participant who develops chronic kidney disease (CKD stage 3b or worse, eGFR<45ml/min) during the study will not be offered further metformin/placebo. The mechanism for reporting and responding to potential adverse events is shown in the safety reporting section 12.4 and 12.5 below.

Chronic metformin use has been associated with Vitamin B12 deficiency [24]. Severe B12 deficiency can result in neuropathic symptoms that can be mistaken for diabetic neuropathy. However, the strength of this association has varied in epidemiologic studies and the clinical significance of mild B12 deficiency syndromes is unclear. The GLINT feasibility phase will measure B12 levels at baseline and 6 month visits. If a participant has a B12 level < 200 pg/ml the results will be reviewed by a study clinician and their GP contacted if necessary. The results will be reviewed following the feasibility phase to inform a decision whether it is necessary to continue monitoring B12 levels in the full study.

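### In the full study a participant can decline GP questionnaires and stay on posted drug; the recurring GP safety reminder and the only planned eGFR request can then lapse

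*Protocol*

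**What the plan says.** Section 9.6.2 sets out staged withdrawal: "Participants can opt to discontinue any or all of the following". The list has four items: study medication, participant questionnaires, "Follow up by GP questionnaires", and registry follow-up.

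Section 9.6.1 gives the protocol-specified reasons for stopping drug. Refusing the participant annual questionnaire is one of them. Refusing the GP questionnaire is not. Investigator judgement is a further route to stopping.

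On the GP reminder, section 12.2.1 says that GPs "will be reminded of contraindications to metformin and this rare side effect and the need to discontinue study medication in these eventualities". It gives three occasions: at study entry, at four months in the feasibility phase, and "annually thereafter when receiving their questionnaire". Section 11.3.1 repeats the link, and its annual mailing is the one used in the full study: participants and GPs are "reminded about the potential risks of taking metformin when they receive their four month questionnaire in the feasibility phase and the annual questionnaire".

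On renal function, the section 6 flow chart ends its list of annual GP items with "most recent eGFR value (if present". Its footnote says "we do not plan to collect creatinine measures during study follow-up", subject to the feasibility safety results, although "we will ask GPs to supply this value if available". Drug stops at eGFR below 45 ml/min (sections 6 and 9.6.1), and 1000 mg a day is the recommended maximum at 45-59 (10.1.1, 10.4). Section 10.4 plans no research visits after baseline once the feasibility phase is complete.

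**The concern.** The protocol ties drug supply to one postal safety channel, the participant questionnaire, but not to the other, the GP questionnaire. The GP channel carries the repeat warning about contraindications and the only scheduled question about kidney function. A participant may drop it and keep receiving tablets.

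The protocol excludes people with eGFR below 45 ml/min, and stops drug at that level, because of the risk of lactic acidosis; repeated GP reminders are part of how it manages that risk. Treatment may last about 7 years (10.1.2), so one letter at entry is a long way from the end of exposure. A participant who develops type 2 diabetes stays on study drug and may have metformin added by the GP (note and Table 1 in 9.6.1), which is a poor time for the reminder to have lapsed.

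The issue is participant safety. Sample size and the primary analysis are not affected.

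**Working it through.** The plan states no figure on this point, so there is none to reproduce. The check follows one full-study participant who declines only the GP questionnaire.

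1. **Does drug stop?** No reason listed in 9.6.1 is met. Supply continues in 16-weekly batches (10.6) unless the investigator decides otherwise.
2. **Is eGFR still requested?** The flow chart puts the request on the GP form. There are no visits and no planned creatinine collection. Planned requests go from one a year to none.
3. **Is the GP still reminded?** Sections 11.3.1 and 12.2.1 both attach the recurring reminder to the questionnaire. If no questionnaire is sent, recurring reminders go from one a year to none. The entry letter has already been sent.
4. **Does anything else replace these?** The electronic record searches in section 13 are optional and look for clinical outcomes. SAE contact (12.5) covers serious illness, assisted hypoglycaemia, admission or stopping drug, so a silent fall in eGFR need not trigger it. Neither is a scheduled eGFR request or a repeat GP warning.

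**Length of the gap for one participant.** The opt-out times are assumptions. The batch interval is 16 × 7 = 112 days, and batches remaining = (years left × 365.25) / 112.

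| Follow-up | Opt-out | GP mailings lost | Batches still posted |
|---|---|---|---|
| 5 years | after year 1 | 4 (years 2-5) | 4 × 365.25 / 112 = 13.0 |
| 5 years | at 2.5 years | 3 (years 3-5) | 2.5 × 365.25 / 112 = 8.2 |
| 5 years | after year 4 | 1 (year 5) | 1 × 365.25 / 112 = 3.3 |
| 7 years | after year 1 | 6 (years 2-7) | 6 × 365.25 / 112 = 19.6 |

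These counts show how long the gap could last. They do not measure renal risk.

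**Number of participants.** The protocol gives no opt-out rate. Section 9.6 expects stopping medication or participation to be rare, but that is a different event from declining the GP form alone. Assuming 0.1% to 1%:

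- 0.001 × 12,898 = 12.9 and 0.01 × 12,898 = 129.0 participants.
- Half are on metformin under 1:1 allocation: 6.4 to 64.5.

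Of these, only people whose eGFR falls below 60 or 45 without their own GP acting would be exposed. The protocol does not allow that number to be estimated.

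**The case against.** The strongest reply on the reminder is that section 12.2.1 promises it to GPs without exception, and that the reference to the questionnaire can be read as timing only. Section 9.6.2 lets a participant drop a data-collection form. It does not list GP contact or safety letters, and consent to GP contact is an entry criterion (9.1). On that reading nothing forbids the reminder after an opt-out. This stands in part: the text does not prohibit the reminder. It also provides no way to send it without the form, so the outcome depends on how staff read two sections.

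On eGFR, the request is thin for everybody. It asks for a value the GP already holds, and only if one exists. It appears in the flow chart but not among the GP items in 11.3.1 or Appendix 1, and a GP who does not return the form causes the same loss. All of this stands. The point takes the flow chart as the intent, and what opt-out removes is the study's own sight of the value.

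A reader might go further and infer that these participants have no renal protection, or that the stop rule fails. The documents do not support that. The participant still gets an annual written reminder about severe illness, including renal failure, and carries an emergency card (12.2.1). Serious illness and admissions must be reported to the centre (12.5). The GP had the entry letter (11.2) and continues ordinary care. The investigator can stop drug (9.6.1) and is expected to explore barriers when someone withdraws (9.6.2).

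**Conclusion.** The point holds in a limited form. In the full study, followed as written, declining the GP questionnaire can end both the recurring GP reminder and the only planned eGFR request while drug is still posted.

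It rests on three assumptions: that the flow chart, rather than the item lists in 11.3.1 and Appendix 1, shows what the GP is asked; that the reminder travels with the form as 11.3.1 and 12.2.1 describe; and that renal monitoring stays as section 6 plans. Section 11.3.2 leaves central renal monitoring to be decided after the feasibility phase. If it is adopted, the eGFR part falls away and the reminder part remains.

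The size is unknown and probably small. Priority is optional: a low-cost safety improvement.

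**What to change.** In 9.6.2 and in item (iii) of 12.2.1, state that the annual GP safety reminder continues for as long as the participant is on study drug, even if GP questionnaires are declined. The letter should give the stop at eGFR below 45 ml/min and the 1000 mg cap at 45-59, and ask the GP to tell the study team if either applies. Add that if the participant also refuses this contact, the investigator reviews under 9.6.1 whether study drug should continue. No automatic stop is needed. The 9.1 consent to GP contact supports the letter.

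The change should not extend to extracting eGFR from the records of every GP who fails to reply. That goes beyond the opt-out problem and would be real work: at an assumed 5% to 20% non-return, 0.05 × 12,898 = 645 to 0.20 × 12,898 = 2,580 record checks a year.

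The cost is amendment wording, a line in the participant leaflet, and, at the assumed opt-out rates, at most about 13 to 129 extra letters a year. The downside is an occasional loss of drug exposure after review, in people who stay under follow-up (Appendix 1, note 5).

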#### **10 Study Treatments**

#### 10.1 Dosage schedules

#### 10.1.1 Route of Administration and Maximum dosage allowed

Metformin comes in prolonged release tablet form for oral administration. The maximum dosage of the study medication will be 1500mg per day.

Participants that have moderate renal impairment (chronic kidney disease stage 3a estimated glomerular filtration rate [eGFR] 45-59 ml/min/1.73m^2) recorded during their participation will be recommended a maximum daily dose of 1000mg metformin prolonged release/placebo.

#### 10.1.2 Maximum duration of treatment of a participant

This is an event driven study and the maximum duration of treatment of a participant is anticipated to be approximately 7 years.

#### 10.1.3 Procedures for monitoring participant compliance

Participants will be instructed to bring all unused or part-used medication and packaging to both the three and six month visits, during the feasibility phase only, so that adherence can be assessed. The study medication will be returned to the participants at those visits. In addition, the four-month questionnaire in the feasibility phase and the annual questionnaire in the full study will include questions which assess compliance with study medication. Data on compliance with study medication will be reviewed during the interim analysis conducted during the feasibility phase of the study.

#### 10.2 Presentation of the drug

One prolonged release tablet contains 500mg metformin hydrochloride corresponding to 390 mg metformin base. It is a white to off-white, capsule-shaped, biconvex tablet, debossed on one side with '500'. The placebo will be created in the image of the active product.

#### 10.3 Known drug reactions & interaction with other therapies

Metformin is a longstanding first-line treatment for T2DM with an excellent safety record. It has also been used in at least 31 trials with 4,570 individuals at risk of developing T2DM followed for 8,267 person-years [23]. In these trials metformin has been associated with substantial beneficial effects on CVD risk factors and risk of T2DM. Refer to Section 12.2 for known drug reactions.

Therapy with metformin should be temporarily discontinued if participants become acutely ill or undergo procedures requiring general anaesthesia or use of iodine containing contrast dye. Metformin must be discontinued 48 hours prior to or at the time of the test and not reinstituted until 48 hours afterwards, and only after renal function has been re-evaluated and found to be normal. Intravascular administration of iodinated contrast media may lead to renal failure, resulting in metformin accumulation and the risk of lactic acidosis.

Alcohol consumption can increase the risk of lactic acidosis, a very rare adverse effect. In the information sheet, participants are therefore advised to avoid drinking lots of

alcohol, both regularly and in short episodes. Participants will be advised not to exceed the Government recommendations; these are 21-28 units of alcohol per week for men and 14-21 units of alcohol per week for women.

Precaution is required when combining metformin with medicinal products with intrinsic hyperglycaemic activity (e.g. glucocorticoids and sympathomimetics). Precaution is also required when combining metformin with diuretics, especially loop diuretics. They may increase the risk of lactic acidosis due to their potential to decrease renal function.

#### 10.4 Dosage modifications

During the treatment period, randomised participants will receive study medication by post in 16-weekly batches. For the first batch following randomisation, individuals will be advised to take 1 tablet/day (500mg metformin prolonged release/placebo) for four weeks, titrating up to 2 tablets/day for weeks 5 to 8, and 3 tablets/day thereafter. Participants will receive a phone call four and eight weeks after randomisation to confirm titration competency. Participants will have contact details of their local research team and the emergency telephone number should they have any queries or experience any serious side effects. Any participants who cannot tolerate 1500mg/day will be advised to take the highest tolerated dose, this will be determined during the titration calls and at the 3 and 6 month visits. Participants will be expected to continue taking study medication for the duration of the study.

Participants that have moderate renal impairment (chronic kidney disease stage 3a estimated glomerular filtration rate [eGFR] 45-59 ml/min/1.73m^2) recorded during their participation will be recommended a maximum daily dose of 1000mg metformin prolonged release/placebo.

During the feasibility phase, research staff will telephone the first 10 participants recruited in each site to enquire as to receipt of the study drug. The DTU will use information from these calls to monitor for any critical failures in the drug delivery process and if they occur will devise an action plan to address underlying causes.

Following completion of the feasibility phase, participants will not be asked to attend any further research visits / health assessments beyond the baseline visit, and will be followed up by post.

If the participant experiences episodes of hypoglycaemia, they will be advised to downtitrate their dose. If they continue to experience hypoglycaemic episodes they will be advised to discontinue the study medication.

#### 10.5 Legal status of the drug

Merck Serono Ltd ([name]) are the marketing authorisation holders of Metformin SR 500mg prolonged release tablets (marketing authorisation number PL 11648/0054). Glucophage SR is currently licensed for use in the treatment of type 2 diabetes mellitus in adults when dietary management and exercise alone does not result in adequate glycaemic control.

The study is being carried out under a Clinical Trial Authorisation. The drug is therefore only to be used by the named investigators, for the participants specified in this protocol, and within the study.

#### 10.6 Drug storage and supply

Investigational materials for the feasibility phase will be provided by Merck Serono as Metformin prolonged release 500mg tablets and matching placebo.

The IMP will be packaged in HDPE bottles with dosing instructions and posted directly to the participants in 16-weekly batches by the drug packager. The IMP does not require any special storage conditions.

#### 10.7 Concomitant therapy

Concomitant medications will be used at the discretion of the participant's usual care provider, who will be informed of the participant's enrolment in the study and the use of blinded study medication. Open label use of metformin is contraindicated during the study except for those participants who develop T2DM during the study where up to a maximum of 1g/day (Table 1) can be prescribed in conjunction with continued study medication.

Any current prescribed medication, other than the study medication, will be recorded at the baseline visit following information from the participant. This information will be updated following receipt of annual questionnaires sent to the participant's GP.

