#### Note:

Participants who develop T2DM during the course of the study should be advised to continue taking study medication and their GP will be advised to consider adding either metformin, such that the daily dose does not exceed the permitted maximum, assuming the study medication is the active therapy (see Table 1), or an alternative glucose lowering drug if required.

GLINT study medication daily dose	Maximum additional daily amount of standard release metformin permitted	Maximum additional daily amount of prolonged release metformin permitted
500 mg (1 tablet)	2000 mg	1500 mg
1000 mg (2 tablets)	1500 mg	1000 mg
1500 mg (3 tablets)	1000 mg	500 mg

Table 1: Prescription of additional metformin for those developing T2DM during the study

Participants who become pregnant during the course of the study can continue taking study medication (28).

Participants who experience a possible CVD event during the study will be encouraged to continue taking study medication as long as there are no contraindications.

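### Section 10.7 allows 1 g/day of added metformin and cites Table 1, but at the full study dose Table 1 allows only 500 mg/day of prolonged release

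*Protocol*

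**What the plan says.** Section 10.7 (Protocol) bars open-label metformin during the study, with one exception. A participant who develops T2DM may receive it, and "up to a maximum of 1g/day (Table 1) can be prescribed in conjunction with continued study medication". The sentence sets no condition on the formulation added or on the number of study tablets taken.

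The Note to section 9.6.1 deals with the same participants. They "should be advised to continue taking study medication and their GP will be advised to consider adding either metformin" or another glucose-lowering drug. Any metformin is to be added "such that the daily dose does not exceed the permitted maximum, assuming the study medication is the active therapy". The details are in "Table 1: Prescription of additional metformin for those developing T2DM during the study", which has three rows (one, two or three study tablets) and two columns (standard-release or prolonged-release add-on).

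Two other places fix which row is usual. Section 10.1.1 states: "The maximum dosage of the study medication will be 1500mg per day". Section 10.4 describes the schedule as "titrating up to 2 tablets/day for weeks 5 to 8, and 3 tablets/day thereafter". Three tablets is therefore both the target and the ceiling. Section 10.4 provides for lower doses in cases of intolerance ("Any participants who cannot tolerate 1500mg/day will be advised to take the highest tolerated dose"), of eGFR 45-59 and of hypoglycaemia.

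**The concern.** Section 10.7 gives one number and names Table 1 as its source, yet Table 1 holds six limits and not all of them equal that number. Both are current protocol text, and no sentence says which governs. The conflict that matters is the one where section 10.7 is the looser text, because there a prescriber who follows it exceeds the limit in the table it cites. That cell lies in the row for the target study dose.

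A written limit carries some weight in this trial. The GP prescribes the add-on without knowing the allocation and is told to dose as if the study drug were active. In the full study there are no research visits after baseline (section 10.4) and no planned collection of follow-up creatinine, although GPs are asked to supply a value if they have one (section 6). The letter to GPs described in section 11.2 must explain what to do if T2DM develops, so whoever drafts it has to choose between the two texts.

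**Working it through.** **Inputs**

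- Flat limit on added metformin: 1 g/day = 1000 mg/day (section 10.7).
- Limits by study dose and formulation: Table 1 (Note to section 9.6.1).
- Target study dose: 1500 mg/day, three tablets (sections 10.1.1 and 10.4).

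**Step 1. Can the 1 g figure be found in Table 1?** Yes, in two cells: two tablets plus prolonged release, and three tablets plus standard release. The second may be where it came from, but section 10.7 does not restrict it to that case.

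**Step 2. Compare every cell.** Difference = Table 1 limit − 1000 mg. A positive value means section 10.7 is stricter; a negative value means it is looser.

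| Study dose | Add-on | Table 1 limit (mg/day) | Difference | Section 10.7 is |
|---|---|---|---|---|
| 500 mg | standard | 2000 | +1000 | stricter |
| 500 mg | prolonged | 1500 | +500 | stricter |
| 1000 mg | standard | 1500 | +500 | stricter |
| 1000 mg | prolonged | 1000 | 0 | equal |
| 1500 mg | standard | 1000 | 0 | equal |
| 1500 mg | prolonged | 500 | −500 | looser |

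Two cells agree, section 10.7 is stricter in three, and it is looser in one. In the looser cell the ratio is 1000 / 500 = 2.

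**Step 3. Totals, treating the study drug as active.** Total = study dose + add-on.

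- Table 1, standard release: 500 + 2000 = 1000 + 1500 = 1500 + 1000 = 2500 mg/day in every row.
- Table 1, prolonged release: 500 + 1500 = 1000 + 1000 = 1500 + 500 = 2000 mg/day in every row.
- Section 10.7 at three tablets, either formulation: 1500 + 1000 = 2500 mg/day.

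Table 1 thus behaves as if it held the total to 2500 mg/day with standard release and 2000 mg/day with prolonged release. The protocol does not state these totals; they are sums. At three tablets with prolonged release, section 10.7 gives 2500 where the table gives 2000 mg/day.

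**Step 4. What each reading permits.** Section 10.7 alone: 1000 mg in all six cells. Table 1 alone: 500 to 2000 mg. The lower of the two: 1000 mg in five cells and 500 mg in one. The three readings are not equivalent.

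**The case against.** The strongest reply is that section 10.7 points to its own correction. A prescriber who follows the citation reaches the row that begins "1500 mg (3 tablets", sees the two limits side by side, and also finds the rule about not exceeding the permitted maximum. The 1 g figure then reads as loose shorthand for the full-dose, standard-release limit. This stands in part: dosing wrongly in the looser cell means acting on section 10.7 without checking the table. The contradiction remains, because the cited table disagrees with the sentence citing it and nothing says which prevails. Taking the lower limit would be safe, but the protocol does not say to do so.

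Four further points on the other side are sound.

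- A reader might infer from two matches in six that four limits are unsafe. Three of the four mismatches have section 10.7 as the more cautious text, so only one cell raises a safety question.
- A reader might take 2500 mg/day as a total that the protocol nowhere accepts. Table 1 accepts it in every standard-release row. Whether the same total matters more with prolonged release depends on labelling that is not in the document.
- A reader might infer that GPs will be told the wrong dose. The GP letter is not shown, so the document cannot settle this.
- A reader might ask for a separate add-on cap at eGFR 45-59. The renal rule in sections 10.1.1 and 10.4 concerns study medication, Table 1 has no renal split, and the document gives no basis for a particular figure.

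**Conclusion.** Wrong as written; minor severity. At three study tablets with a prolonged-release add-on, section 10.7 permits 1000 mg/day where the table it cites permits 500 mg/day. The other three mismatches are ambiguity, with section 10.7 stricter by 1000, 500 and 500 mg/day.

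Reach is narrow. The conflict needs incident T2DM, a GP who adds metformin and not an alternative drug, a prolonged-release product, and a participant on the full study dose. The document does not give the number who would meet all four conditions, and no harm can be quantified from it. Sample size and primary analysis do not depend on this limit.

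The conclusion rests on reading section 10.7 as it stands, with its limit applying to either formulation and to any study dose.

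**What to change.** Reword the limit in section 10.7 along these lines: *no more than 1 g/day, and never above the Table 1 limit for the participant's study dose and metformin formulation (500 mg/day of prolonged release at three tablets)*. Make the GP letter described in section 11.2 carry the same limit.

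This lowers the permitted add-on in the one looser cell and loosens no limit, so it needs no renal footnote. It does mean that the three Table 1 entries above 1000 mg (2000, 1500 and 1500) would no longer be reached.

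If the sponsor intends Table 1 alone to govern, the 1 g figure should be deleted. Compared with section 10.7, that raises the permitted add-on in three cells, by 1000, 500 and 500 mg/day, so it should be a deliberate clinical decision and not a tidying edit.

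The drafting cost is one sentence and a check of the letter. As it changes a prescribing limit, it would go through as a protocol amendment, with steering committee approval (section 17.1) and sponsor agreement before submission (section 18.4). Data collection, sample size and analysis are unchanged.
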